##### **B. Description of Population to be Enrolled:**

- a. Pediatric patients birth to 18 years of age
- b. Patients on all pediatric and neonatal inpatient units at Roosevelt Hospital
- c. First positive blood cultures on admission or during hospitalization

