- e. We will compare time to optimal antimicrobial therapy (primary outcome), as well as secondary outcome measures, between the intervention group and the 2 control groups (historical controls, as well as concurrent controls).

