**D. Description, Risks and Justification of Procedures and Data Collection Tools:**

The panel will be performed all on positive pediatric blood cultures that are positive during laboratory working hours. The panel results will be released to clinical providers. This is necessary in order to assess the clinical impact and clinical decision-making based on the results. A local investigator will review all positives throughout the day and inform the treatment team of the results. All enrolled patients will undergo chart review to assess for clinical outcomes, such as antimicrobial agents, ICU days, hospital days, and mortality. We will need to collect this information in order to assess the clinical impact of this panel. The information will be stored directly into RedCap database which will be accessible only to key study personnel. The study involves minimal risk to the patient, as it only includes risk of loss of confidentiality. We are requesting a full waiver of informed consent, as subjects will be assigned to the intervention versus control group based on the timing of positive cultures. Patients, providers and investigators will not have control over which patients will be placed into the control or intervention groups, as this will be randomized based on time of positivity. This reflects the reality of laboratory capabilities in low-middle income countries, such as Guatemala.

**E. Potential Scientific Problems:** There will be challenges of working in Guatemala City, as this is a limited-resource setting. The culture around antibiotic usage is different than in the U.S. and therefore may impact the expected reduction in time to effective and optimal antimicrobial therapy. Currently they only obtain a single blood culture bottle during collection, but this is standard in many low-middle income countries.

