Rapid Blood Culture Identification Panel in Pediatric Patients in Guatemala

NCT05314816

Statistical Analysis Plan

v. 2/23/2023

Statistical Analysis Plan

Objective: to evaluate the clinical impact of the BioFire BCID2 panel in children with bacteremia in Guatemala.

Study Design: Pragmatic clinical trial comparing intervention to two different control groups. Intervention and concurrent control group allocated by time of blood culture positivity. Also comparing to historical controls.

Primary outcome: time to optimal antimicrobial therapy

Secondary outcomes:

- Time to effective antimicrobial therapy
- Time to pathogen identification
- Mortality
- Length of hospital stay
- Antibiotic days of therapy (DOT)
- Number of unique antibiotics
- Total ICU days

Definitions to consider:

Patient Group

Intervention= patient was enrolled in the intervention group and received the BCID2 intervention within 12h timeframe

Concurrent control= patient was enrolled in the study and did not receive the BCID2 intervention within 12h from blood culture positivity

- Weekday controls= Patient with positive blood culture from 1pm-11:59pm Mon-Thurs
- Weekend controls= Patient with positive blood culture from 1pm Fri- 11:59pm Sunday

Per protocol =patient received intervention based on original allocation.

- Per protocol intervention= Patient allocated to intervention based on timing of blood culture AND BCID2 was performed within 8h timeframe.
- Per protocol control= Patient allocated to control group based on timing of blood culture AND no BCID2 was performed.

Protocol deviation=Patient intended to remain in the allocated group, but there was an unintentional deviation from protocol.

- Protocol deviation intervention= BCID2 run between 8-12h in patient allocated to intervention.
- Protocol deviation control= BCID2 was sent clinically >12h from positive culture in patient allocated to control group OR patient originally allocated to intervention group but BCID2 was not performed.

Sub-groups

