Clinician discretion (Intention to treat analysis (ITT))=effective and optimal therapy determined based on whether **treating physicians** considered the pathogen real or a contaminant. Optimal therapy allowed additional antibiotics if the treating team was also treating for other syndromic diagnoses, such as culture-negative sepsis (if pathogen detected deemed to be a contaminant), nosocomial pneumonia, etc. if called out in diagnoses. Definitions created for optimal therapy for nosocomial pneumonia, culture-negative sepsis, etc.

- Time to effective therapy in ITT:
 - Time from blood culture received in lab (time 0) to effective therapy
 - Time from blood culture positivity (time 0) to effective therapy
- Time to optimal therapy in ITT:
 - Time from blood culture received in lab (time 0) to effective therapy
 - Time from blood culture positivity (time 0) to effective therapy

Pathogen directed (Per protocol analysis) =effective and optimal therapy based on **strict definitions** for real pathogen or contaminant created by study team. Strict optimal antibiotic definitions without allowing for additional antibiotics for culture-negative sepsis or nosocomial pneumonia, etc. Does allow for additional antibiotics for clear other indications (pyelonephritis, CAP, dacrocystitis, intra-abdominal abscess, etc.) or another organism isolated (excluding urine and trach cultures). Not allowing for more controversial diagnoses such as sepsis or nosocomial pneumonia.

- Time to effective therapy in per protocol:
 - Time from blood culture received in lab (time 0) to effective therapy
 - Time from blood culture positivity (time 0) to effective therapy
- Time to optimal therapy in per protocol:
 - Time from blood culture received in lab (time 0) to effective therapy
 - Time from blood culture positivity (time 0) to effective therapy

Secondary outcomes

Time to pathogen identification= Time from time of blood culture receipt in lab (time 0) to identification of a pathogen. For control patients, this is the time to Vitek. For intervention patients, this is the time to BCID2 if the BCID2 was positive for an on-panel pathogen or time to vitek if the BCID2 was negative.

- Control: time to Vitek
- Intervention:
 - If BCID2 positive → calculate time to BCID2 result
 - If BCID2 negative → calculate time to Vitek

Total antibiotic days=all days that patient was on antibiotics (any dose of antibiotic) from date that blood culture was drawn. Capped at 14 days or date of death.

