Antibiotic days of therapy =Sum of antibiotics each day over 14-day period. For example if 2 antibiotics were each given over 5 days, this would count as 10 DOT.

Number of different antibiotics=Number of unique antibiotics given over the 14-day period.

Length of stay=date admitted to date patient left the study (date of death/discharge or lapse of 30 days). Censor at 30 days.

Total ICU days=date admitted in ICU to date transferred out or date of death/discharge. Censor at 30 days.

Time to death= Time from blood culture obtained to time of death.

Number of deaths within 24h of blood culture draw= Use time of death calculation above to determine the number of patients who died <24h

Overview of Analyses to perform:

- All interventions vs. all concurrent controls (including protocol deviations) vs. historical controls
 - Demographics
 - All outcomes (primary and all secondary endpoints)
 - Sensitivity analysis comparing weekday vs. weekend controls
- Per protocol controls vs. per protocol intervention (excluding protocol deviations)
 - Demographics
 - All outcomes (primary and all secondary endpoints)
- Clinician discretion (ITT) analysis (controls vs. interventions)

- Number of contaminants vs. true pathogens
- Time to optimal therapy
- Time to effective therapy
- Pathogen directed (Per protocol) analysis (controls vs. interventions)
 - Number of contaminants vs. true pathogens
 - Time to optimal therapy
 - Time to effective therapy
- Gram negatives only (on- and off- panel)
 - Demographics
 - Time to optimal therapy
 - Time to effective therapy
 - Mortality
- On-panel true pathogens only
 - Demographics
 - Time to optimal therapy
 - Time to effective therapy
 - Mortality
- On-panel Gram negatives only
 - Demographics
 - Time to optimal therapy
 - Time to effective therapy
 - Mortality
- True pathogens (on and off panel)
 - Demographics
 - Time to optimal therapy
 - Time to effective therapy
 - Mortality

Figure 1: CONSORT Diagram

Table 1: Patient Characteristics

*Wilcoxon test of medians

**chi-square test

Table 1A: Supplemental table with demographics from sub-groups.

	Per protocol Intervention	Per protocol Control	p-value	True on-panel pathogen Intervention	True on-panel Pathogen controls	p-value	All Gram negative (GN) Interv.	All GN control	p-value	All GN weekDAY controls	p-value (compare to GN interv.)	On-panel GN Interv.	On-panel GN control	p-value

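### Length of stay and ICU days include days before culture positivity and treat death like discharge, so a group difference in them cannot be read as a panel effect

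*SAP*

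**What the plan says.** The SAP's secondary-outcome definitions give, for stay, "Length of stay=date admitted to date patient left the study (date of death/discharge or lapse of 30 days", and for intensive care, "Total ICU days=date admitted in ICU to date transferred out or date of death/discharge. Censor at 30 days". Length of stay is also censored at 30 days. Neither definition says from which date the 30 days run.

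The SAP's study design statement fixes when groups form: "Intervention and concurrent control group allocated by time of blood culture positivity". Protocol IV.B admits "First positive blood cultures on admission or during hospitalization" and covers "Patients on all pediatric and neonatal inpatient units at Roosevelt Hospital", so positivity can come long after hospital or ICU admission.

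Both outcomes enter group comparisons. Protocol IV.C.e compares the primary outcome, "as well as secondary outcome measures, between the intervention group and the 2 control groups", and the SAP's overview of analyses applies all secondary endpoints to the intervention, concurrent and historical groups. Protocol IV.A lists the two outcomes without defining them, and lists hospital and ICU days again under the exploratory cost analysis.

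Other outcomes start at the culture: "Total antibiotic days=all days that patient was on antibiotics (any dose of antibiotic) from date that blood culture was drawn". Time to death also starts there, and the SAP's Figures section already plans curves with positivity as time zero. Neither document gives a positivity-based start or a competing-event rule for stay or ICU days.

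**The concern.** There are three faults in the definitions.

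- **Start.** A newborn whose culture turns positive in the third week brings all earlier days into length of stay. None of them can respond to a test run after positivity. For ICU days this applies only to children already in the ICU at positivity. For cultures taken at admission, the extra time is little more than incubation.
- **End.** A death and a discharge home on the same day give the same value. If the panel changed mortality, stay would change even if no survivor went home sooner or later.
- **Limit.** If the 30 days run from admission, a child cultured on day 20 has 30 − 20 = 10 observable days left. If they run from the culture, a stay counted from admission can exceed 30 days, and the censoring instruction is unclear.

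What is at stake is how two secondary outcomes are read. The primary outcome is not touched.

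**Working it through.** **Inputs.** From the documents: 20% mortality in the historical cohort (Protocol III), and group sizes of 135, 219 and 99 (SAP Table 2). Everything else is assumed. The documents give no expected value, spread or power for stay or ICU days, so there is no plan figure to reproduce. The test for these outcomes cannot be read because the body of Table 3 is missing from the text; a rank-sum test on values capped at 30 days is assumed.

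**1. Effect of death alone.** Let survivors' stay be lognormal and the same in both groups, with (median, log-SD) = (10, 0.5), (10, 0.7), (14, 0.5), (14, 0.7). The median stay x of a group with mortality m solves

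(1 − m)·F_surv(x) + m·F_death(x) = 0.5.

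Example: survivors' median 10, deaths' median 5, log-SD 0.5. At m = 0.20, x = 8.88; at m = 0.10, x = 9.46; change +0.58 days. Over the four settings, change in median stay in days:

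| Timing of deaths | 20% to 10% | 20% to 15% |
|---|---|---|
| Deaths' median half the survivors' | +0.58 to +0.84 | +0.29 to +0.42 |
| Equal | 0 | 0 |
| Double | −0.69 to −1.02 | −0.36 to −0.53 |

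The bounds are all deaths before the median (survivors' quantile (0.5 − m)/(1 − m): 0.375 at 20%, 0.444 at 10%), giving +0.80 to +1.49; and all deaths after it (quantile 0.5/(1 − m): 0.625, then 0.556), giving −1.00 to −2.06.

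**2. Precision, groups balanced.** Simulation of 135 v 219. Time to positivity is 2 days for all, plus a gamma time (shape 1.5, mean 5 or 10 days) for the 30% or 50% who are hospital-onset. Post-positivity stay is lognormal, median 10, log-SD 0.6, and 20% shorter in the intervention group.

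| Case | From positivity | From admission |
|---|---|---|
| No deaths | about 91% power | 62 to 84% |
| 20% die in both groups, median 3 days after positivity | about 57% (discharge alive) | 39 to 57% |

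In the second row, deaths are ranked as never discharged in the positivity analysis. Repeat runs gave 53 to 58% and 38 to 57%. The gain is therefore between about 57 − 57 = 0 and 57 − 39 = 18 points. With no true difference, both analyses reject in about 5% of trials.

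**3. Groups not balanced.** Let the hospital-onset share differ by 10 points, with no deaths and no panel effect. From admission, the capped median shifts by 0.5 to 1.1 days and false positives are 9 to 15% (v 219) or 8 to 12% (v 99). From positivity they stay at about 5%, but only if post-positivity stay is unrelated to onset type. If hospital-onset children also stay 1.5 to 2 times longer after positivity, the positivity analysis gives about 7 to 16% (v 219), against 15 to 28% from admission.

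**The case against.** - **Admission to discharge is the ordinary meaning of hospital stay, and it serves the cost analysis.** This stands. The written outcomes should be kept, not replaced, all the more because group sizes are already filled in.
- **Balanced pre-positivity days are only noise.** Also true. A reader might infer that the comparison is biased as written; the documents do not show that. They give no hospital-onset share by group. Equally, allocation by clock time and the use of historical controls do not guarantee balance, and the characteristics readable in Table 1A include neither onset type nor time from admission to culture.
- **Mortality is reported separately, and NICU and non-NICU children have their own tables (3A, 3B).** Separate mortality reveals the problem but leaves it inside the stay comparison. Splitting by unit changes neither the start nor the handling of death.
- **The gain from re-anchoring is easily overstated.** This stands. The no-death contrast of 91% with 62 to 84% does not describe the recommended analysis in a cohort with 20% mortality; there the gain may be nil. Nor does starting at positivity remove other case-mix differences.
- **A halving of mortality is a large effect.** Agreed; a fall to 15% gives about half the shift.

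A reader might also infer that better survival must look like a longer stay. It need not: the sign depends on whether deaths come early or late relative to discharge, and the documents do not give that timing.

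**Conclusion.** The concern holds for the definitions as written, and no other section corrects them. Stay and ICU days can include time before the panel could act, death and discharge are not told apart, and the 30-day limit has no stated start. A difference between groups in either outcome therefore cannot be read as benefit or harm from the panel.

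The likely size is modest: a few tenths of a day to about one day in median stay in the half-to-double scenarios, in either direction, and a power loss from nothing to about 18 points when 20% die early. These figures rest on assumed stay distributions, death timing, hospital-onset share and a rank-sum test. Confidence is high for the definitions and does not extend to the size of any effect. Only secondary outcomes are affected. The change should be made, chiefly so that the comparison has a clear meaning.

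**What to change.** By a dated SAP change, labelled as added after group sizes were known:

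1. **Stay.** Add time from culture positivity to discharge alive, with a 30-day horizon from positivity and death as a competing event. Show cumulative incidence by group and compare groups with Gray's test.
2. **ICU.** Add days alive and out of the ICU from positivity to day 30 for every child, counting repeat ICU stays against the total, with deaths given zero days (or ranked worst).
3. **Early events.** State one rule, the same in all groups, for children who died or were discharged before positivity, and report their number by group.
4. **Limit.** State where the current 30 days start.
5. **Written outcomes.** Keep them as defined, reported as total stay and total ICU days and for the cost analysis, and say that a difference in them is not read as a panel effect.

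Cost: extra analysis. Positivity time is already needed for the planned curves, which include historical controls. If the current limit runs from admission, dates after day 30 may not have been collected: a child cultured on day 20 needs dates to day 20 + 30 = 50. That could mean more chart review, including the 99 historical charts. The method is already in Protocol IV.D: "All enrolled patients will undergo chart review to assess for clinical outcomes, such as antimicrobial agents, ICU days, hospital days, and mortality".
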